#### 20.6. Reports to the IRB/Ethics Committee (EC)

Before study initiation, the investigator must have written and dated approval from the IRB for the protocol, consent form, patient recruitment materials /process (e.g., advertisements), and any other written information to be provided to patient. The investigator should also provide the IRB with a copy of the Investigator's Brochure and/or package insert. The investigator should provide the IRB with reports, updates, and other information (e.g., safety updates, protocol amendments, and administrative letters) according to regulatory requirements or Institution procedures.

#### 20.7. Quality Assurance Audits

Representatives from Sponsor and/or a third party selected by Sponsor may conduct a quality assurance audit of this study. During the audit, the Investigator must provide the auditor with direct access to all relevant documents and discuss any findings with the auditor.

In the event of an inspection by the Food and Drug Administration or other regulatory authorities, the Investigator will notify the Sponsor /CRO as soon as possible of such notice and must give the inspector direct access to relevant documents and discuss any findings with the inspector.

#### 20.8. Records Retention

The investigator must maintain records of the study product disposition, copies of the case report forms and all source documents for the maximum period of five years after NDA approval as required by Sponsor. The investigator must contact Sponsor prior to destroying any records associated with this study.

If the location of the study files changes from the address noted on the FDA Form 1572, written notification of the new location must be given to Sponsor. If the investigator withdraws from participation in the study the records shall be transferred to a mutually agreed-to designee. Written notification of such a transfer must be given to Sponsor.

**APPENDIX 2: PRO – PAPSS**

[figure not shown]

### **APPENDIX 3: PRO – PAPI**

[figure not shown]

[figure not shown]
**APPENDIX 4: PRO – PGI-S**

[figure not shown]
**APPENDIX 5: PRO – PGI-C**

[figure not shown]
**APPENDIX 6: PRO – PGI-TS**

**APPENDIX 7: PRO – PGI-SE**

**APPENDIX 8: ROSACEA QUALITY OF LIFE QUESTIONNAIRE  
(ROSAQOL)**

© Emory University

12. INDEX OF PLANNED TABLES39

13. INDEX OF PLANNED FIGURES150

14. INDEX OF PLANNED LISTINGS157

1. LIST OF ABBREVIATIONS AND DEFINITIONS OF TERMS

AE(s)	adverse event(s)
ANCOVA	analysis of covariance
ANOVA	analysis of variance
ATC	Anatomical Therapeutic Chemical
BMI	body mass index
C	Celsius
cm	centimeters
CRF(s)	case report form(s)
eCRF(s)	electronic case report form(s)
E-BPO	encapsulated benzoyl peroxide
FDA	Food and Drug Administration
GCP	good clinical practice
IGA	Investigator Global Assessment
ITT	Intent-to-Treat
IWRS	Interactive Web Response System
kg	kilograms
LOCF	last observation carried forward
LSMean or LSM	least square mean
max	maximum
MCMC	Markov Chain Monte Carlo
MedDRA	Medical Dictionary for Regulatory Activities
mg	milligram
min	minimum
n	number of observations
N	number of subjects (sample size)
PAPI	Patient Assessment of Papulopustular rosacea Impacts
PAPSS	Patient Assessment of Papulopustular Rosacea Signs and Symptoms
PGI-C	Patient Global Impression of Change
PGI-S	Patient Global Impression of Symptom Severity
PGI-SE	Patient Global Impression of Treatments Side Effects
PGI-TS	Patient Global Impression of Treatments Satisfaction
PP	per-protocol

PT	preferred term
QST	QST Consultations, Ltd.
RosQoL	Rosacea Quality-of-Life
SAE(s)	serious adverse event(s)
SAS®	Statistical Analysis System (SAS® Institute Inc., Cary, NC)
SD	standard deviation
SOC	system organ class
TEAE(s)	treatment-emergent adverse event(s)
WHO	World Health Organization

2. PREFACE

This Statistical Analysis Plan (SAP) describes the statistical analyses as it is foreseen before breaking the blind. The SAP will serve as a compliment to the study protocol and supersedes it in case of differences. In case of major differences between the study protocol and SAP, e.g. changes in the analysis related to the primary endpoint, a protocol amendment will be considered. The SAP may be updated during the study conduct and will be finalized before breaking the blind.

The following documents were reviewed in preparation of this SAP:

- Clinical Study Protocol SGT-54-01
 - Version 1.0 issued on 14MAR2018,
 - Version 2.0 issued on 30APR2018,
 - Version 3.0 issued on 07JUN2018,
 - Version 4.0 issued on 08NOV2018
- Case report form (CRF) for SGT-54-01.
- ICH E9 Guidance on Statistical Principles for Clinical Trials.
- ICH E3 Structure and Content of Clinical Study Reports (CSRs)

The reader of this SAP is encouraged to also read the clinical protocol for details on the conduct of this study, and the operational aspects of clinical assessments and timing for completing a patient in this study.

3. RESPONSIBILITIES

The study statistician will be responsible for the statistical analysis planning. QST Consultations, Ltd. (QST), a Contract Research Organization (CRO) selected by Sol-Gel, will be responsible for the execution of all statistical programming deliverables. The statistical programming work will be supervised by the study statistician.

4. INTRODUCTION

S5G4T-1 is an innovative topical formulation containing 5% encapsulated benzoyl peroxide (E-BPO) that Sol-Gel is developing for the treatment of papulopustular rosacea. If approved, S5G4T-1 will be the first product containing E-BPO for the treatment of papulopustular rosacea. Sol-Gel believes S5G4T-1 has the potential to be as tolerable as, and more effective than, currently marketed rosacea drugs.

Rosacea is a chronic and recurrent inflammatory dermatological disorder of unknown etiology. The disease is common, especially in fair-skinned people of Celtic and northern European heritage. The onset of the disorder is usually between the ages of 30 and 50. Early stages of the disease affect women more often than men at a ratio of 3 to 1 [1, 2]. Rosacea usually starts as flushing and subtle redness on the cheeks, nose, chin or forehead. Alcohol, hot drinks, spicy foods, stress, sunlight and extreme heat or cold can trigger the onset of this disease. If left untreated, rosacea can slowly worsen over time. As the condition progresses, patients experience inflammatory lesions (papules and pustules), vivid erythema and telangiectasia. Patients may develop furuncles, cystic nodules, granulomas and tissue hypertrophy, sometimes leading to rhinophyma.

Rosacea is treated with both systemic and topical therapies. However, topical therapies are preferable because of side effects caused by the use of systemic therapies.

According to the U.S. National Rosacea Society, approximately 16 million people in the United States are affected by rosacea. According to a study commissioned by the Sponsor, approximately 4.8 million people in the United States experience subtype II symptoms and physicians estimate that only 20% of the U.S. rosacea population is treated. The topical drugs approved by the Food and Drug Administration (FDA) to treat subtype II rosacea generated aggregate revenues of approximately \$392 million in the United States for the 12 months period ending June 30, 2017.

In August 2012, Sol-Gel completed a double blind, randomized, dose-ranging Phase 2 trial for S5G4T-1 involving 92 adult patients at ten centers in the United States (SGT-EBPO1-09: A Multi-Center, Double-Blind, Randomized, Vehicle-Controlled, Dose-Range Study of

Encapsulated Benzoyl Peroxide Gel, 1% and 5%, and Vehicle Gel in the Treatment of Rosacea). The Phase 2 trial had two co-primary endpoints: success in Investigator Global Assessment (IGA) namely, a two-grade reduction in IGA on a scale of 0 to 4 ("clear", "almost clear", "mild", "moderate", "severe") with clear or almost clear at Week 12; and a reduction in the mean inflammatory lesion count at Week 12 (end of trial). The second co-primary endpoint was the change from Baseline in the inflammatory lesions (papules and pustules) count at end of trial. All patients were 18 years of age or older with 12 or more inflammatory lesions at enrollment. Patients were randomly divided into three groups of 30 to 32 patients each and received a once daily dose, with one group receiving S5G4T-1 (E-BPO 5%), a second group receiving a 1% concentration of E-BPO and a third control group receiving the vehicle (placebo) alone. The evaluator rated the following signs of local skin irritation on a scale of 0 to 3 ("none", "mild", "moderate", "severe") for dryness and scaling. Information on adverse events (AEs) was also collected.

Both E-BPO 1% and S5G4T-1 demonstrated statistically significant improvement in comparison to the vehicle in reducing papulopustular lesions based on the percentage change in the inflammatory lesion count from Baseline at Week 12, $p = 0.014$ and $p = 0.02$, respectively, and S5G4T-1 also demonstrated statistically significant improvement in comparison to the vehicle in achieving the IGA success co-primary endpoint ($p = 0.0013$). All three formulations were well tolerated. A few patients had moderate local application site irritation (dryness, scaling, pruritus, stinging and burning) during treatment.

A clear trend of dose response with IGA success of 20.0% for the vehicle, 37.5% for the E-BPO 1% and 53.3% for S5G4T-1 was observed. Both S5G4T-1 and E-BPO 1% significantly reduced the number of inflammatory lesions with a trend towards dose response indicated by median reduction of 10 lesions in the vehicle group compared to 12.5 and 15 in the E-BPO 1% and S5G4T-1 groups, respectively.

5. STUDY OBJECTIVES

The primary objectives of this pivotal study are:

- To assess the efficacy and safety of S5G4T-1 compared to S5G4T-1 Vehicle when applied once daily for 12 weeks in patients with papulopustular rosacea.

5.1 Secondary Objective

The secondary objective of this pivotal study is:

- To demonstrate statistical superiority in efficacy of S5G4T-1 compared to the vehicle with regard to percent change from baseline.

5.2 Supportive Objective

The supportive objective of this pivotal study is:

- To determine the time required to observe improvement in the efficacy parameters associated with clearance of rosacea for S5G4T-1 compared to vehicle.

5.3 Safety Objective

The safety objectives of this pivotal study are:

- To determine the nature, severity and frequency of the adverse event rate, the Cutaneous Safety Assessment and the Local Tolerability Assessment of S5G4T-1 compared to the vehicle.

6. STUDY DESIGN

6.1 Overall Study Design

This study will be a randomized, double-blind, multicenter, parallel group, active- and vehicle-controlled pivotal study of the efficacy and safety of S5G4T-1 and its vehicle for the treatment of papulopustular rosacea for 12 weeks. Approximately 350 patients with moderate to severe rosacea (rated 3 or 4 on the 5-point IGA scale) will be enrolled at up to 28 sites. Patients in this randomized, double-blind, vehicle-controlled, parallel-group multi-center study will be randomly assigned in a 2:1 ratio to S5G4T-1 or vehicle, respectively. Subjects with severe rosacea who are appropriate for systemic treatment need to be counseled regarding their treatment options by the Principal Investigator.

Patients will receive once daily treatment with S5G4T-1 or vehicle cream for 12 weeks. After the screening period, qualified patients will be randomly assigned at the Baseline visit and treated for 12 weeks. Efficacy assessments will include facial inflammatory lesion counts and IGA assessment ranging from 0 (clear) to 4 (severe). Investigators will be provided with instructions for lesion counts to ensure consistency of procedure. Patient reported outcomes (PRO) will be assessed with the PAPSS (Patient Assessment of Papulopustular Rosacea Signs and Symptoms), PAPI (Patient Assessment of Papulopustular rosacea Impacts), and PGI-S (Patient Global Impression of Symptom Severity) that will be administered at Baseline, Weeks 2, 4, 8, and 12, or at early termination. In addition, the PGI-C (Patient Global Impression of Change), PGI-TS (Patient Global Impression of Treatments Satisfaction), and PGI-SE (Patient Global Impression of Treatments Side Effects) will be administered at Weeks 2, 4, 8, and 12, or at early termination [FDA Guidance 2009]. Safety will be assessed at all visits and will include monitoring local and systemic adverse events (AEs); the Investigator Cutaneous Safety Assessment rating of

erythema, dryness and scaling, and the Local Tolerability Assessments rating of itching and burning/stinging on a scale ranging from 0 (none) to 3 (severe).

Patients will return to centers for IGA, lesion counts, PRO questionnaire, Investigator Cutaneous Safety Assessment, and Local Tolerability Assessments at Weeks 2, 4, 8 and 12. AEs and concomitant medications will be assessed throughout the treatment period. A urine pregnancy test is required at Visit 1, 2, 4, 5, and 6 for all females of child-bearing potential.

Clinical Evaluations will be performed at:

- Visit 1/Screening
- Visit 2/Baseline, Day 1
- Visit 3/Week 2, Day 15 (\pm 3 Days)
- Visit 4/Week 4, Day 29 (\pm 3 Days)
- Visit 5/Week 8, Day 57 (\pm 3 Days)
- Visit 6/Week 12, Day 85 (\pm 4 Days)/End of Treatment)

6.1.1 Schedule of Visits and Assessments

The schedule of assessments can be found in Section 13.9 of the protocol.

6.1.2 Method of Assigning Subjects to Treatment Groups

Patients who satisfy all the inclusion and none of the exclusion criteria will be randomized to one of two treatment arms. Randomization will be performed in the Interactive Web Response System (IWRS) according to a computer-generated randomization schedule. The randomization schedule will be generated by the unblinded statistician and uploaded to the IWRS. The randomization schedule will be maintained securely within the IWRS. Patients will be randomized to E-BPO 5% or vehicle cream, once daily on a 2:1 basis for twelve (12) weeks.

Once a patient is determined eligible for the study at the Baseline visit, the patient will be randomized to study product assignment by the IWRS. Each study product carton will contain four pumps of the same product; The first supplied pump in each kit is marked A (e.g. number of pump within a kit is XXXXA), at Visit 4/ Week 4 the patient will return the pump and will be dispensed with the next pump which is marked B. At Visit 5/ Week 8, the patient will be dispensed with a pump marked C. The pump marked as D is a backup pump. The patient number will be added to both parts of the kit label (open part and tear-off label and to the pump label).

6.1.3 Blinding

The staff involved in data management and statistical evaluation will remain blinded until identification of the analysis population is completed and a database lock memo is issued.

The randomization schedule and treatment code will not be revealed to the patients, study personnel, Sol-Gel or its representatives until after the database lock, except to the Medical Monitor or Principal Investigator for an emergency. Access to the randomization list will be maintained by and limited to the unblinded Biostatistician and the designated personnel directly responsible for labeling of study materials. The Medical Monitor will not have access to the randomization list, but may determine that unblinding one or all patients may be necessary in the case that the safety of study patients is at risk. In an emergency, the study blind may be broken only if:

- In the opinion of the Medical Monitor and/or the Principal Investigator, it is in the patient's best interest to do so
- Knowledge of the treatment will alter the clinical management of the patient

In the case of an emergency that requires unblinding, the Investigator can request to unblind the patient without prior contact with the Medical Monitor although follow-up between the Investigator and Medical Monitor must occur so that all parties are aware of the unblinding. Although it is recommended that the Investigator contact the Medical Monitor prior to unblinding any patient, in instances where this is not feasible or advisable the Principal Investigator may directly access the patient's treatment assignment. In all situations, the IWRS will be used to obtain treatment assignment information with limited access to only the above-designated individuals, and any unblinding will be documented as a protocol deviation.

7. EFFICACY AND SAFETY ENDPOINTS

7.1 Efficacy Endpoints

7.1.1 Primary Efficacy Endpoints

There are two co-primary efficacy endpoints:

- Proportion of patients with the primary measure of success (clear or almost clear) in IGA relative to Baseline at Week 12
- Absolute change in inflammatory lesion counts from Baseline to Week 12

7.1.2 Secondary Efficacy Endpoints

The secondary efficacy endpoints are as follows:

- Percent change in inflammatory lesion count from Baseline to Week 12
- Absolute change in inflammatory lesion count from Baseline to Week 8
- Proportion of patients with the primary measure of success (clear or almost clear) in the IGA relative to Baseline at Week 8
- Absolute change in inflammatory lesion count from Baseline to Week 4
- Proportion of patients with the primary measure of success (clear or almost clear) in the IGA relative to Baseline at Week 4

7.1.3 Additional Supportive Efficacy Endpoints

The supportive efficacy endpoints include the following:

- Percent change in inflammatory lesion count at Week 8
- Percent change in inflammatory lesion count at Week 4
- Mean change comparison in PAPSS item 1 (burning) between groups from Baseline to Weeks 4, 8 and 12
- Mean change comparison in PAPSS item 2 (itching) between groups from Baseline to Weeks 4, 8 and 12
- Mean change comparison in PAPSS item 3 (redness) between groups from Baseline to Weeks 4, 8 and 12
- Mean change comparison in PAPSS item 4 (bumps) between groups from Baseline to Weeks 4, 8 and 12
- Rosacea erythema assessment at Week 12
- Telangiectasia assessment at Week 12
- The proportion of patients in treatment relative to control who report at least “minimally improved” (defined as “very much improved”, “much improved” or “minimally improved”) as measured by the PGI-C at Week 12
- Mean change in the components of the PAPI score between groups from Baseline to Week 12

- Proportion of patients in the treatment relative to control achieving a three-point improvement in the components of the PAPI score from Baseline to Week 12
- PGI-S at Week 12
- PGI-TS at Week 12
- PAPSS within-person absolute change from Baseline to Week 12 (and/or other, earlier time points if so desired)

Other supportive endpoints not outlined in the SAP will be explored by Sol-Gel as appropriate.

7.1.4 Exploratory Endpoints

The exploratory endpoint is the mean change in Rosacea Quality-of-Life (RosaQoL) subscale scores from Baseline to Week 12.

7.2 Safety Endpoints

Safety will be assessed through Cutaneous Safety Assessment, Local Tolerability Assessment, AE reporting, physical examination, vital signs, and PGI-SE.

8. STATISTICAL AND ANALYTICAL PLANS

8.1 General Methodology

All statistical processing will be performed using SAS® version 9.3 or later unless otherwise stated. Statistical significance will be based on two-tailed tests of the null hypothesis resulting in p-values of 0.05 or less. These methods are intended to analyze the results of the study.

The primary method of handling missing efficacy data will be based on estimation using the method of Markov Chain Monte Carlo (MCMC) imputation. This method provides robust estimation when the pattern of missingness is arbitrary. Additionally, the estimation will be done for each treatment group separately so that the pattern of missingness for one group does not influence the estimation of missing data for another group. Groups of complete datasets following the estimation will be concatenated to form analysis datasets for the comparative analyses and subsequent imputation result inference with SAS PROC MIANALYZE.

Descriptive statistics will also be derived from the multiply imputed datasets.

Additionally, a model-based multiple imputation process will be used as a sensitivity analysis to the MCMC imputation. Finally, the absolute change in lesion count will be analyzed using a repeated measures analysis of covariance (ANCOVA) for lesion count data and a repeated measures logistic regression model (generalized estimating equations) for the dichotomized IGA.

8.1.1 Statistical Analysis

All analyses will be performed by QST using SAS® Version 9.3 or later. All summary tables and data listings will be prepared utilizing SAS® software.

The standard operating procedures (SOPs) of QST will be followed in the creation and quality control of all data displays and analyses.

All data listings will be by subject. Additionally, all listings except the screen failure and randomization listings will be by treatment.

8.1.2 Baseline Definition

Baseline is defined as the last non-missing assessment prior to first application of study drug. If the date of first application is unknown due to the subject being lost to follow-up, the Baseline visit record will be used as Baseline if it is non-missing. Missing results will not be flagged as Baseline.

8.1.3 Visit Windowing

Data will be summarized based on nominal visit indications with the exception of data captured at early termination and unscheduled visits. Data from early termination and unscheduled visits will be summarized based on mapped visit values. The analysis windows for early termination and unscheduled visits are presented in the following table.

Analysis Windows for Efficacy and Safety Assessments

Scheduled Visit	Target Study Day	Window (Days)
Week 2	15	8 to 21
Week 4	29	22 to 42
Week 8	57	43 to 70
Week 12	85	71 to 98

Data collected at early termination and unscheduled visits prior to study day 8 will not be analyzed, with the exception of those identified as Baseline values. Data collected at early termination and unscheduled visits after study day 98 will not be included in analyses.

The definition for the study day included in each study window is defined as below:

Study Day prior to Day 1 = Visit Date – Day 1 Date

Study Day on or after Day 1 = Visit Date – Day 1 Date + 1

If an assessment's mapped visit is a visit at which the subject has data from a scheduled visit present, or if no analyses are planned for the assessment at the mapped visit, the data collected at the early termination or unscheduled visit will not be included in analyses.

In the event of multiple values from unscheduled or early termination assessments within an analysis window, the value closest to the scheduled visit target study day will be used for analyses. If two values tie as closest to the time point (for example, one value is before and the other value is after the time point), then the later value will be selected.

Data collected at all visits will be included in the data listings with visit presented as reported by the site.

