- Patient Global Impression of Symptom Severity (PGI-S) at Week 12
- Patient Global Impression of Treatment Satisfaction (PGI-TS) at Week 12.
- A set of cumulative distribution function (CDF) curves will be generated to allow for the evaluation of within-person change by treatment group. Specifically, 5 plots will be generated showing the change from baseline to Week 12 [and/or other, earlier time points if so desired] by the cumulative percent of subjects for each of the treatment arms (change on the x-axis will be expressed as absolute change) on:
  - PAPSS total scale scores;
  - PAPSS item 1 (burning) scores;
  - PAPSS item 2 (itching) scores;
  - PAPSS item 3 (redness) scores; and
  - PAPSS item 4 (bumps) scores

- **The safety objective of this pivotal study is:**

The safety objectives of this study are to determine the nature, severity and frequency of the adverse event rate, the Cutaneous Safety Assessment and the Local Tolerability Assessment of S5G4T-1 compared to the vehicle.

The safety endpoints to be assessed include the following:

- Adverse events (AEs), including serious adverse events (SAEs) occurring at any time during the trial.
- Investigator Cutaneous Safety Assessment and Local Tolerability Assessments score at any time during the trial.

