## 16.2. Local Tolerability Assessments

The evaluator will assess local application site tolerability by rating the itching and burning/stinging at the Baseline visit and site visits at Weeks 2, 4, 8 and 12 (End of Study) or unscheduled visits. The evaluator will determine the score for each of these variables by asking the patient to grade their experience over the **past 24 hours**. The definitions of grades provided in [Table 5](#) will be applied to these evaluations. The Local Tolerability Assessment evaluations of itching and burning/stinging will be made by the investigator at the time of the visit.

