**Table 5: Local Tolerability Assessment Scale**

Grade	Description
Itching	
0 – None	No itching
1 – Mild	Slight itching, not really bothersome
2 – Moderate	Definite itching that is somewhat bothersome
3 – Severe	Intense itching that may interrupt daily activities and/or sleep
Burning/Stinging	
0 – None	No burning/stinging
1 – Mild	Slight burning/stinging sensation; not really bothersome
2 – Moderate	Definite warm, burning/stinging sensation that is somewhat bothersome
3 – Severe	Hot burning sensation that causes definite discomfort and may interrupt daily activities or sleep

Application site reactions (itching and burning/stinging) are not to be recorded as adverse events unless they result in either:

- The temporary discontinuation of the study product.
- The discontinuation of the patient from the study.
- The use of a new concomitant medication in order to treat this event.

Any other application site reaction not listed above should be recorded as adverse events in the source document and eCRFs.

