8.8.4.2 Local Tolerability Assessments

Descriptive statistics by treatment group and visit will be provided for itching and burning/stinging.

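### Off-schedule tolerability peaks can miss every score summary, although the protocol's safety endpoint covers the score at any time

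*SAP*

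**What the plan says.** Protocol section 8 and the synopsis list two safety endpoints. One is adverse events. The other is the "Investigator Cutaneous Safety Assessment and Local Tolerability Assessments score at any time during the trial". Protocol 16.2 has the evaluator "rating the itching and burning/stinging at the Baseline visit and site visits at Weeks 2, 4, 8 and 12 (End of Study) or unscheduled visits"; section 16.1 has the same visit schedule for dryness and scaling. All four signs are graded 0 to 3.

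SAP 7.2 names the same assessments without the time qualifier: "Safety will be assessed through Cutaneous Safety Assessment, Local Tolerability Assessment, AE reporting, physical examination, vital signs, and PGI-SE".

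SAP 8.1.3 sets analysis windows that apply to safety as well as efficacy assessments. Three of its rules remove ratings:

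- Early cut-off: "Data collected at early termination and unscheduled visits prior to study day 8 will not be analyzed, with the exception of those identified as Baseline".
- Late cut-off: early-termination and unscheduled data after Day 98 are excluded.
- Displacement: where the visit to which a rating maps already has scheduled data, "the data collected at the early termination or unscheduled visit will not be included in analyses".

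If several off-schedule values compete for an empty window, the one nearest the target day is used, not the worst. Every rating is still listed.

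The planned summary of itching and burning is: "Descriptive statistics by treatment group and visit will be provided for itching and burning/stinging". SAP 8.8.4.1 says the same for dryness and scaling. Table 14.3.1.1 gives grade frequencies at Baseline and Weeks 2, 4, 8 and 12.

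The adverse event rule sits under Protocol Table 5: "Application site reactions (itching and burning/stinging) are not to be recorded as adverse events unless they result in either" a temporary stop of the product, the patient leaving the study, or a new medication to treat the reaction. Table 4 carries the same rule for dryness and scaling.

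**The concern.** The endpoint spans the whole trial and the protocol pays for it by collecting ratings between visits. The SAP then builds the summary from scheduled visits almost alone. An unscheduled visit is a likely occasion for a patient to show a reaction, so the excluded ratings may be the informative ones.

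The scheduled ratings cannot stand in for them. Itching and burning/stinging are graded over the preceding 24 hours (Protocol 16.2), so four post-baseline visits sample about four days of a 12-week treatment. The first is due on Day 15 ± 3, so no scheduled post-baseline rating falls before Day 12.

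At stake is how completely the report describes local tolerability. The protocol's introduction describes burning and itching as familiar effects of benzoyl peroxide.

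**Working it through.** The plan states no figure on this point, so there is nothing to reproduce. The check applies the SAP 8.1.3 rules day by day and then follows each excluded rating to wherever else it could appear.

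**Inputs.** Analysis windows from SAP 8.1.3; visit windows from the protocol's study flow chart.

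| Visit | Target day | Protocol visit window | Analysis window |
|---|---|---|---|
| Week 2 | 15 | 12–18 | 8–21 |
| Week 4 | 29 | 26–32 | 22–42 |
| Week 8 | 57 | 54–60 | 43–70 |
| Week 12 | 85 | 81–89 | 71–98 |

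The analysis windows cover Days 8–98 without a gap, and each protocol visit window lies inside its analysis window.

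**Step 1: days on which an unscheduled rating can enter a by-visit table.** Sum (last day − first day + 1) over the windows that hold no scheduled rating.

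- All four visits rated: 0 days.
- Only Week 2 missed: 21 − 8 + 1 = 14 days.
- Only Week 4 missed: 42 − 22 + 1 = 21 days.
- Only Week 2 attended: 98 − 22 + 1 = 77 days.
- No post-baseline visit attended: 98 − 8 + 1 = 91 days.

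**Step 2: early-termination ratings.** A post-baseline rating before Day 8 is never analysable. Suppose a patient attends exactly on target days and then leaves. The termination rating is excluded on Days 2–7 (6 days), 16–21 (6), 30–42 (13) and 58–70 (13). That is 6 + 6 + 13 + 13 = 38 of the 83 days from Day 2 to Day 84, or 38/83 = 46%. On 6 + 13 + 13 = 32 of those 38 days the window already holds a scheduled rating. This is a share of calendar days under one attendance pattern, not a share of patients or ratings.

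**Step 3: where the excluded ratings can still appear.**

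- *Reaction still present at a scheduled visit, any grade:* in Table 14.3.1.1.
- *Reaction that interrupts the product, ends participation or needs a new medication:* recorded as an adverse event. SAP 8.8.2 defines treatment-emergent events by onset relative to first application, not by visit window, and Table 14.3.1.2.1 has rows for stopping the drug and leaving the study because of one. The event is graded on the general severity scale of Protocol 17.2; its off-schedule 0–3 score can still be excluded.
- *Off-schedule peak that meets none of the three conditions and has subsided by the scheduled visit:* Listing 16.2.7.1 only.

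An example of the last case is grade 3 burning/stinging at an unscheduled Day 5 visit, in a patient who carries on without interruption or new medication. The adverse event rule does not record it, the Day 8 cut-off removes the score, and no maximum is planned. The same peak at an unscheduled visit on Day 36, after a Week 4 visit on Day 29, maps to Days 22–42 and is displaced.

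**The case against.** The strongest reply is that the wording promises less than it seems to. The same time qualifier is attached to adverse events, can be read as the collection period, and nowhere mentions a maximum. Protocol 19.5 itself plans descriptive statistics by scheduled visit for dryness and scaling, and the SAP's preface says the SAP prevails where the two differ. This stands as far as it goes: a worst-grade analysis was not promised. But under the collection-period reading, ratings collected inside that period still enter no score summary, and SAP section 10 does not list this narrowing among the changes.

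A reader might infer that the worst local reactions reach no summary table at all. The documents do not support that. Severe reactions at scheduled visits are tabulated, and those that cause interruption, withdrawal or new treatment must be recorded as adverse events and reach tables that use no visit window.

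A reader might also infer that intolerance is understated mainly in the active arm. The protocol's introduction does tie these effects to benzoyl peroxide, but it also reports irritation in both groups of one early study. SAP section 4 describes all three Phase 2 formulations as well tolerated. Neither passage shows an imbalance in off-schedule ratings. Nor do the documents say why the adverse event rule was written as it is.

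A further worry would be that frequencies by visit confuse disease relief with drug irritation. Table 14.3.1.1 shows Baseline beside each visit and has a randomised vehicle arm, and patient-reported burning and itching (PAPSS) are tabulated with change from Baseline. That answers most of this worry, but those questionnaires are scheduled at the same visits and do not catch peaks between them.

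Finally, a maximum depends partly on how often a patient returns. That is true, and the added table should say so.

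**Conclusion.** The gap is real and narrow. The by-visit tables do not describe the tolerability score over the whole trial, because off-schedule ratings are cut off or displaced and no worst post-baseline grade is planned. For a patient rated at all four post-baseline visits, every post-baseline unscheduled score is excluded from the tables; before Day 8 every post-baseline early-termination score is excluded too. What is lost altogether from summaries is an off-schedule peak, up to grade 3, that meets none of the three adverse-event conditions and is gone by the scheduled visit. For more consequential reactions the event is kept but the 0–3 score may not be.

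This rests on SAP 8.1.3 being applied as written and on the ratings being completed at the scheduled visits attended. The number of patients affected and any difference between arms cannot be computed: the documents give no expected frequency of unscheduled visits or of withdrawals before Day 8. The 46% figure must not be read as either. The output concerned is descriptive, so no hypothesis test is affected. It is a cheap improvement worth making.

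**What to change.** In SAP 8.1.3, exempt the cutaneous and local tolerability scores from the exclusions for the purpose of one added Safety-population table. For each of dryness, scaling, itching and burning/stinging, the table gives by arm the highest post-baseline grade and the largest worsening from Baseline over all ratings: scheduled, unscheduled and early termination. Leave Table 14.3.1.1 unchanged, and record the addition in SAP section 10. A footnote should state that a maximum depends partly on how many unscheduled visits a patient makes; the number of ratings per patient by arm would let the reader judge this.

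The cost is a short SAP edit and one more descriptive table from data already collected. Reported irritation rates may look slightly less favourable.
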